4. A detailed description or list of all secondary data elements and/or secondary specimens that will be obtained and how they will be used (if applicable)

See the help text for additional guidance

Participants will first be screened via phone or online, via a multi-study screening process/registry described in HM 20002567 (see attachment "Registry consent form and questions"). Participants can tell study staff if they are interested in screening for a particular study only. All screening data collected from participants who choose to join the registry will be used in this study. Participants who appear eligible will then be scheduled for an in-person screening visit where they will provide informed consent if they choose to participate and complete other forms (see in-person screening forms: ICF, Health Information Form, Penn State Cigarette Dependence Index, and FTND. These will be completed on paper forms or via RedCap). Participants will also be able to view other questionnaires (Direct Effects of Product Questionnaire, Direct Effects of Nicotine Questionnaire, Tiffany-Drobes QSU, Hughes-Hatsukami Questionnaire - listed as Subjectives - 1-4 in documents), via computer, and the study equipment. Women will be excluded if they are breast-feeding or test positive for pregnancy (by urinalysis) at screening. After screening and informed consent, eligible participants will enroll in this study, which is modeled on our previous work (e.g., Spindle et al., 2016). A total of 30 participants are needed to complete the study.

Once enrolled, participants will attend the lab for three additional experimental sessions where they will use the JUUL, IQOS, and own brand cigarettes. Participants will use each of the three products, using one product during a single session. For example, a participant may use the JUUL for the first session, own brand cigarettes for the second session, and the IQOS for the last session. Order of the products used in each session will be assigned using Latin-

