- The procedures that will be followed to collect the sample
- The role(s) of the individuals who will collect the sample
- The volume/size range of the sample
- The timing and frequency of sample collection

Urine will be collected at screening to test for pregnancy (women only). Urine will not be stored for later use.

Upon arrival at the CBPL/CSTP for the research session, participants' breath CO will be measured to ensure compliance with the overnight abstinence criteria (i.e. CO < 10 ppm; see Breland et al., 2006). CO will also be measured before and after bouts to be analyzed as a study outcome measure (change in CO before and after bouts).

Blood will be collected via intravenous catheter 4 times at each session (7 ml each time), for a total of 12 samples per person in the entire study (84 ml in total). Blood will not be collected more than 2 times per week.

6. * Will genetic testing or analyses be conducted on any of the samples:

- Yes
- No

ID: HM20012013

View: SF2 - Active Internet Data Collection

Active Internet Data Collection

1. * Describe the platform/technology chosen for collecting the data and transmitting data securely over the Internet. Give the rationale for selecting this technology.

The in-person screening questionnaires and questionnaires administered during sessions may be administered via RedCap or via paper forms. All of the data will be stored in REDCap, and viewing will be restricted to those personnel associated with this protocol (listed under personnel).

2. * Describe how data will be linked or unlinked to identifiers including email addresses, names, and/or IP address.

Data will be linked (via a key stored in a separate location) to participant IDs and dates of birth.

3. * Is there an alternative method for completion of the data collection other than the Internet?

- Yes
- No

4. * If yes, describe the alternative(s).

Paper forms.

5. * Describe how individuals will be able to skip or not answer particular questions. If any questions are mandatory, provide justification.

Participants will be able to skip any question.

6. If not including children, describe any procedures used to verify that research participants are adults.

We ask participants for their age and date of birth several times (telephone or online screening, in-person screening) and verify that the answers are the same.

ID: HM20012013

View: SF2 - Secondary Data/Specimen Details

Secondary Data/Specimen Details

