10. * Is the original consent form that participants signed upon entry into the registry / repository available?

- Yes
 No

11. If NO above, describe in detail the allowed uses of the data information/specimens as outlined in the registry / repository consent. Be sure to describe any stipulations or limitations on the use.

12. If YES, the original consent is available, upload it for the IRB to reference

ID: HM20012013

View: SF2 - Costs to Participants

Costs to Participants

1. * Select all categories of costs that participants or their insurance companies will be responsible for:

- Participants will have no costs associated with this study
 Study related procedures that would be done under standard of care
 Study related procedures not associated with standard of care
 Administration of drugs / devices
 Study drugs or devices
 Other

2. * Provide details of all financial costs to the participant, other than time and transportation. Additional details regarding standard of care costs will be requested on another screen, if applicable.

There are no other financial costs to the participant, other than time and transportation.

ID: HM20012013

View: SF2 - Compensation

Compensation

1. * Describe any compensation that will be provided including:

1. total monetary amount
2. type (e.g., gift card, cash, check, merchandise, drawing, extra class credit)
3. how it will be disbursed

Participants will receive \$75 after completing the first session, \$100 after completing the second session, and \$125 after completing the third session (not counting the first lab visit for the in-person screening). Thus, the total amount participants could earn for the entire study is \$300. If a participant chooses to leave the study early, he or she will keep the amount earned up to that point. In addition, if a session must be discontinued for reasons beyond the control of the participant, the participant will be paid for the time spent complying with study conditions before the session began (\$15) and also the time spent in the laboratory (\$15/hour). All payments will be in the form of cash.

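### In the visible protocol, adult age is checked only by whether self-reported age and birth date agree, so a false date given consistently would pass

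*Protocol*

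**What the plan says.** Active Internet Data Collection, item 6, puts this request to the investigators: "If not including children, describe any procedures used to verify that research participants are adults". The reply is one sentence, saying that staff ask for "age and date of birth several times (telephone or online screening, in-person screening) and verify that the answers are the same". Nothing else is offered as an age check.

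Study Procedures, item 7, gives the two occasions on which the answers are collected. The first is remote: "Participants will first be screened via phone or online, via a multi-study screening process/registry described in HM 20002567". The second is a visit: "Participants who appear eligible will then be scheduled for an in-person screening visit where they will provide informed consent". That item lists what is completed at the visit: the consent form, a health form, two dependence questionnaires and, for women, a urine pregnancy test. No age or identity document is mentioned.

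The Consent Process page has each participant sign for themselves, with no waiver requested. Compensation, item 1, sets payments of $75, $100 and $125 for the three sessions and adds: "All payments will be in the form of cash".

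**The concern.** Item 6 asks for verification and the answer describes a consistency check. The two differ in exactly the case that matters. A person who knows that adulthood is required, and who wants to take part, has reason to invent one birth date and repeat it.

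The setting gives that person a motive and a route. Recruitment is open, through flyers, newspapers and internet postings; the first screen is remote; and payment is in cash. If such a person were enrolled, a minor would have signed a consent form meant for adults, used nicotine products in up to three sessions and had a catheter placed for research only. At stake are the protection of that person and the validity of that consent.

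**Working it through.** No formula in the plan bears on this and there is no plan figure to reproduce. The check is a reading of the sections side by side, then the logic of the stated rule.

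**Step 1. What each visible section contributes to establishing age**

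| Protocol section | What it provides | Independent of self-report? |
|---|---|---|
| Active Internet Data Collection, item 6 | Age and birth date asked repeatedly and compared | No |
| Study Procedures, item 7 (phone or online screen) | Answers given to the registry questionnaire | No |
| Study Procedures, item 7 (in-person screen) | Forms, questionnaires, pregnancy test | No age check described |
| Secondary Data/Specimen Details, item 1 | Contact details and eligibility answers from the registry | No |
| Consent Process | Participant's own signature | No |
| Risks, Discomforts, Potential Harms and Monitoring, item 2 | Seizure and cardiovascular precautions | No age check described |

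**Step 2. What the rule can detect**

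The rule flags an applicant only if the answers differ between occasions, or if the stated age does not fit the stated birth date. Let *c* be the share of under-age applicants who give the same false date, with a matching age, each time. Then

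- detection among under-age applicants ≤ 1 − *c*;
- detection among those who answer consistently = 0, by construction.

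The protocol gives no value for *c*, so it is an assumption and the whole range is shown:

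| Assumed *c* | Detected, at most |
|---|---|
| 0 | 100% |
| 0.5 | 50% |
| 1 | 0% |

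The protocol also gives no figure for how many under-age people might apply, so the expected number enrolled cannot be calculated.

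**Step 3. How the protocol treats other self-reports**

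Overnight abstinence is not taken on trust: breath carbon monoxide must be below 10 ppm on arrival. Pregnancy is tested in urine at screening. Adult age, on which the participant's own consent depends, has no comparable objective check in the visible text, although every participant attends in person before enrolment.

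**Step 4. Payment**

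75 + 100 + 125 = 300, which agrees with the protocol's stated total of $300.

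**The case against.** The strongest reply is that the visible text may not be the whole of the procedure. Item 6 sits on a page about internet data collection, not on an eligibility page. Several blocks in Study Population are redacted. First-line screening runs under HM20002567, which is not shown, and neither is the health form used in person. The check marks on the lists of identifiers and on the Social Security Number question are lost, so those lists show nothing either way. An identity check could exist in any of these places. This stands, and it limits the point to the visible protocol. It does not remove the point, because item 6 asks for any procedure used and names just this one.

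A second reply is that staff meet each participant face to face at screening and at three sessions. That is a partial, informal safeguard, but the protocol does not present it as an age check.

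A third is that nothing here is contradictory and no standard in the document requires photo ID. That is true. The point is that the stated procedure cannot do what the item asks of it, not that a rule has been broken.

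A reader might also infer three stronger conclusions, which the document does not support:

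- *That the seizure risk makes minors a group of special concern here.* The only basis is the wording of a web address in the risk section, which names young adults together with youth. The notice itself is not available, and the protocol lists its own seizure precautions.
- *That each case costs the trial data.* One of 30 completers is 1/30 = 3.3%, but up to 75 people may be consented to reach 30 completers, so a case found during enrolment could be replaced within that limit. The protocol does not say that such data must be removed; it describes removal at the participant's request.
- *That minors were enrolled.* Nothing shows this.

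**Conclusion.** The point holds for the visible protocol. The one procedure stated for confirming adulthood compares self-reports with each other, and its ability to detect a false date repeated consistently is zero. This is a weakness in participant protection and consent validity. It does not bear on the endpoints, sample size, power or analysis.

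Its practical size is unknown, since neither the number of under-age applicants nor the share who would answer consistently is given. The conclusion rests on two assumptions: that the reply to item 6 is complete, as the question invites, and that neither the redacted text nor HM20002567 contains an independent check. If either does, the remaining fault is only that item 6 fails to cite it. The change is worth making because it costs little and uses a visit that already takes place.

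**What to change.** Replace the reply to item 6 with wording to this effect:

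> At the in-person screening visit, before consent, staff view a photo ID and confirm that the date of birth shows adult age and matches the date given at phone or online screening. This applies whether or not the applicant joined the registry. No copy of the ID is kept.

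The match should be to the screening answer, not to a registry entry, because Study Procedures, item 7, allows people to screen for one study without joining the registry. Keep the existing agreement check as a pre-screen.

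If HM20002567 already requires an independent age check, a citation to it in item 6 is enough.

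The cost is a brief check at a visit already scheduled and a line asking applicants to bring ID. The downside is that those who arrive without it must be rescheduled.
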